- At any time after the initiation of therapy, loss of CHR, CCyR or PCyR.
- At any time after the initiation of therapy, detection of new BCR-ABL1 mutations which potentially cause resistance to study treatment (asciminib or bosutinib).
- At any time after the initiation of therapy, confirmed loss of MMR in 2 consecutive tests.
- At any time after the initiation of therapy, new clonal chromosome abnormalities in Ph+ cells: CCA/Ph+.

Conditions preventing patients to switch to asciminib

- Any Grade 3 or 4 toxicity which has not resolved to Grade 2 or lower within 28 days and before starting asciminib treatment.
- Asymptomatic (Grade 2) pancreatitis if not resolved within 28 days
- Disease progression while on bosutinib treatment. The following events are considered disease progression:
 - Accelerated phase (AP) as defined by any of the following:
 - $\geq 15\%$ blasts in the peripheral blood or bone marrow aspirate, but $< 30\%$ blasts in both the peripheral blood and bone marrow aspirate.
 - $\geq 30\%$ blasts plus promyelocytes in peripheral blood or bone marrow aspirate.
 - $\geq 20\%$ basophils in the peripheral blood.
 - Thrombocytopenia ($< 100 \times 10^9/L$) that is unrelated to therapy.
 - Blast crisis (BC) as defined by any of the following:
 - $\geq 30\%$ blasts in peripheral blood or bone marrow aspirate
 - Appearance of extramedullary involvement other than hepatosplenomegaly proven by biopsy (i.e. chloroma).
- QTcF at time of switch > 480 msec or inability to determine QTc interval

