7.1.2.2 Conditions to be fulfilled for asciminib switch

The eligibility assessments of patients who are candidates for asciminib switch will start with the bosutinib EOT visit. Assessments conducted during the EOT visit will be used to evaluate if all conditions for asciminib switch are fulfilled and there are no conditions preventing patients from receiving asciminib treatment. Therefore all efforts **MUST** be made to ensure that all EOT assessments are completed per [Table 7-1](#). In the event that all EOT assessments cannot be completed during the EOT visit, they must be completed within 42 days (6 weeks) after the bosutinib EOT visit. For details of assessments required for patients that switch treatment from bosutinib to asciminib, please refer to [Table 7-2](#). The maximum allowed time frame for patients failing bosutinib to start treatment with asciminib is 42 days after bosutinib EOT.

In case a patient presents with a grade 3 or 4 adverse event at the time of the EOT visit or develops it after the EOT visit, the adverse event must be resolved to grade 2 or lower before starting asciminib treatment and within 28 days of the date of occurrence of the adverse event as outlined in the criteria listed below.

However, a patient who has laboratory test (peripheral blood test) results or ECG results that do not satisfy the treatment switch conditions may have the tests repeated multiple times during the treatment switch screening period. The last test performed before start of asciminib dosing must meet the conditions for treatment switch as listed below.

If a patient does not meet the conditions for treatment switch, they should enter the survival follow-up phase.

The conditions for treatment switch will be checked via the IRT system. Please refer and comply with detailed guidelines in the IRT manual.

Conditions to fulfill to allow the switch to asciminib:

1. Failure to bosutinib treatment up to 96 weeks after the last patient received the first dose (adapted from the 2013 ELN Guidelines; [Baccarani et al 2013](#)). Patients must meet at least 1 of the following criteria. Failure is defined as follows:
 - Three months after the initiation of therapy or thereafter: No CHR or > 95% Ph+ metaphases.
 - Six months after the initiation of therapy or thereafter: BCR-ABL1 ratio > 10% IS and/or > 65% Ph+ metaphases.
 - Twelve months after initiation of therapy or thereafter: BCR-ABL1 ratio > 10% IS and/or > 35% Ph+ metaphases.

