- At any time after the initiation of therapy, loss of CHR, CCyR or PCyR.
- At any time after the initiation of therapy, detection of new BCR-ABL1 mutations which potentially cause resistance to study treatment (asciminib or bosutinib).
- At any time after the initiation of therapy, confirmed loss of MMR in 2 consecutive tests.
- At any time after the initiation of therapy, new clonal chromosome abnormalities in Ph+ cells: CCA/Ph+.

Conditions preventing patients to switch to asciminib

- Any Grade 3 or 4 toxicity which has not resolved to Grade 2 or lower within 28 days and before starting asciminib treatment.
- Asymptomatic (Grade 2) pancreatitis if not resolved within 28 days
- Disease progression while on bosutinib treatment. The following events are considered disease progression:
 - Accelerated phase (AP) as defined by any of the following:
 - $\geq 15\%$ blasts in the peripheral blood or bone marrow aspirate, but $< 30\%$ blasts in both the peripheral blood and bone marrow aspirate.
 - $\geq 30\%$ blasts plus promyelocytes in peripheral blood or bone marrow aspirate.
 - $\geq 20\%$ basophils in the peripheral blood.
 - Thrombocytopenia ($< 100 \times 10^9/L$) that is unrelated to therapy.
 - Blast crisis (BC) as defined by any of the following:
 - $\geq 30\%$ blasts in peripheral blood or bone marrow aspirate
 - Appearance of extramedullary involvement other than hepatosplenomegaly proven by biopsy (i.e. chloroma).
- QTcF at time of switch > 480 msec or inability to determine QTc interval

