4. Action taken with respect to study or investigational treatment (none, dose adjusted, temporarily interrupted, permanently discontinued, unknown, not applicable)

5. Whether medication or therapy was given (no concomitant medication/non-drug therapy, concomitant medication/non-drug therapy)
6. Whether it is serious, where a serious adverse event (SAE) is defined as in [Section 8.2.1](#) and which seriousness criteria have been met
7. Outcome (not recovered/not resolved, recovered/resolved, recovering/resolving, recovered/resolved with sequelae, fatal, unknown)

If the event worsens the event should be reported a second time in the eCRF noting the start date when the event worsens in toxicity. For grade 3 and 4 adverse events only, if improvement to a lower grade is determined a new entry for this event should be reported in the eCRF noting the start date when the event improved from having been Grade 3 or Grade 4.

All adverse events should be treated appropriately. If a concomitant medication or non-drug therapy is given, this action should be recorded on the Adverse Event eCRF.

Once an adverse event is detected, it should be followed until its resolution or until it is judged to be permanent, and assessment should be made at each visit (or more frequently, if necessary) of any changes in severity, the suspected relationship to the study treatment, the interventions required to treat it, and the outcome.

Natural progression or deterioration of the malignancy under treatment (including loss of response, progression to accelerated phase or blast crisis and death due to disease progression), will be recorded as part of the efficacy evaluation and should NOT be reported as an AE/SAE.

Signs and symptoms clearly associated with the disease under study should NOT be reported as AEs unless they are newly emergent (i.e. not previously observed in the patient), judged by the Investigator to be unusually severe or accelerated, or if the Investigator considers deterioration of disease-related signs and symptoms to be caused directly by the study drug. If there is any uncertainty about an AE being due solely to the disease under study, it should be reported as an AE or SAE as appropriate.

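### The AP/BC bar to the asciminib switch is limited to time on bosutinib, although the first asciminib dose may come up to 42 days after bosutinib ends

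*Combined protocol and SAP*

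**What the plan says.** Section 7.1.2.2 sets out who may move from bosutinib to asciminib after treatment failure. On timing it states: "The maximum allowed time frame for patients failing bosutinib to start treatment with asciminib is 42 days after bosutinib EOT". The decision rests on the EOT assessments. Any that cannot be done at the EOT visit may be completed within the same 42 days.

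Four conditions prevent the switch. The progression condition is introduced by "Disease progression while on bosutinib treatment. The following events are considered disease progression", followed by four AP criteria and two BC criteria. The protocol summary repeats it.

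The section allows peripheral-blood tests and ECGs that fail the switch conditions to be repeated, and adds: "The last test performed before start of asciminib dosing must meet the conditions for treatment switch as listed below". On ineligible patients it says: "If a patient does not meet the conditions for treatment switch, they should enter the survival follow-up phase".

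**The concern.** The progression bar carries a time limit that ends with bosutinib treatment, but eligibility is still being worked up after that point. A patient may be untreated for weeks after failing at least a third TKI. Section 2.6 already describes patients who have failed two prior TKIs as being at increased risk of AP and BC. If blasts rise in that interval, or if an EOT marrow completed late is the first evidence of AP/BC, the finding was not made on bosutinib and the list does not exclude the patient.

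Two things are at stake. A patient in advanced phase could start asciminib without breaching a listed condition, and Section 7.1.6 would then require the drug to be stopped. Also, one dose places the patient in the Switch Analysis Set (Section 10.1.6). Safety after bosutinib failure is a secondary objective in Table 3-1 and efficacy after failure is an exploratory one. Both could then mix chronic-phase and advanced-phase patients.

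**Working it through.** The plan gives no figure on this point to reproduce. The check is mainly of wording, with one ceiling calculation.

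**1. How far each bar in Section 7.1.2.2 runs**

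| Bar | Time limit |
|---|---|
| Grade 3–4 toxicity | Must have resolved "within 28 days and before starting asciminib treatment" |
| Asymptomatic grade 2 pancreatitis | 28 days to resolve; not tied to the first dose |
| AP/BC | "Disease progression while on bosutinib treatment" |
| QTcF | "QTcF at time of switch > 480 msec or inability to determine QTc interval" |

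Two of the other three bars run to the switch. The section also deals expressly with grade 3–4 events that develop after EOT. It has no matching sentence for progression.

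**2. Whether another rule fills the interval**

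- *Last-test rule.* It refers back to the listed conditions, so it may import either their thresholds alone or their time limit as well. It concerns blood tests and ECGs, so marrow and biopsy findings fall outside it on either reading.
- *Toxicity bar.* Under Section 8.1.1, disease deterioration including "progression to accelerated phase or blast crisis and death due to disease progression), will be recorded as part of the efficacy evaluation" and is not to be reported as an AE. AP/BC as such therefore does not trigger this bar.
- *Section 7.1.6.* It requires study treatment to stop on progression, and Section 4.1.1 applies it to switched patients. It governs stopping, not starting.
- *Schedule.* Table 7-2 has an extramedullary check at S-Screening and S-Week 1 Day 1, and haematology at S-Week 1 Day 1. S-Screening haematology is needed only if it was not done at EOT. These checks can detect AP/BC, but no listed condition acts on the result.
- *Discretion.* Section 2.2 leaves the switch to the investigator's judgement of the patient's best interest. That is a safeguard in practice, but not an eligibility condition.

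**3. Ceiling on the uncovered time**

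Inputs: 74 planned bosutinib patients (Section 10.8); 42 days (Section 7.1.2.2). Assumption: every bosutinib patient switches, each on the last allowed day, counting from EOT as the plan does.

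74 × 42 = 3,108 days; 3,108 / 365.25 = 8.5 patient-years.

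Using the 233 patients actually randomised (amendment 03-US.01): 233 / 3 ≈ 78; 78 × 42 = 3,276 days; 3,276 / 365.25 = 9.0 patient-years. The conclusion is the same.

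The true figure is smaller, because not all patients fail and switch, and few would wait the full 42 days. The documents give no off-drug AP/BC rate, so no number of cases follows.

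**4. Which criteria a blood result can meet**

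Listed criteria: 4 AP + 2 BC = 6. A peripheral-blood value can contribute to 5: blasts, blasts plus promyelocytes, basophils and platelets for AP, and blasts for BC. The platelet criterion also requires the thrombocytopenia to be unrelated to therapy, so a count alone does not settle it; that leaves 5 − 1 = 4. Three criteria (AP blasts, AP blasts plus promyelocytes, BC blasts) can also be met on marrow alone, and extramedullary disease needs a biopsy. The last-test rule does not reach findings of these last two kinds.

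**5. Endpoints**

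A switching patient has discontinued randomised bosutinib. Sections 10.4.3 and 10.5.1 make that patient a non-responder for MMR at a later time point, and in Section 10.5.2 discontinuation is itself a TTF event. PFS counts documented AP/BC as the event, including during survival follow-up.

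**The case against.** The strongest answer is that the section should be read as a whole. EOT assessments may be completed up to 42 days late in order to judge the switch conditions. It would be odd if a late marrow or blood count could not inform the progression condition. On that view the last-test rule points to the listed thresholds, and the bar covers progression found at any time in the switch evaluation. This is a fair reading and probably the intended one. What remains is that the words do not say it, and that the last-test rule covers only blood tests and ECGs.

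Some stronger readings do not hold:

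- A reader might infer that trial entry is stricter than the switch. The documents do not support this. Section 5.2 applies its cut-offs at the screening visit, which may be 21 days before Week 1 Day 1, and the marrow may be 56 days old (Section 7.1.2). Entry does not require freedom from AP/BC at first dose either.
- A reader might infer that the toxicity bar can never catch these patients. Section 8.1.1 allows newly emergent or unusually severe disease signs to be reported as AEs, so a new grade 3–4 cytopenia accompanying AP/BC may be caught.
- A reader might infer that the IRT would let such a patient through. The check is defined in a manual outside these documents, so this is unknown.

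It is also fair that most such patients would be noticed and not dosed. As of 15-Oct-2018 the sponsor counted only 4 patients who could have used the switch.

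**Conclusion.** The point stands in a narrow form. Read literally, AP/BC first arising or first documented between the end of bosutinib and the first asciminib dose is not a listed bar. For the blood criteria the last-test rule makes this ambiguous; for marrow and extramedullary findings nothing listed fills the gap. Severity is low.

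A reader might infer a threat to the main efficacy results. There is none: MMR at 24 and 96 weeks, TTF on randomised treatment and PFS are unaffected. The effect is confined to patient safety at the switch and to the composition of the descriptive safety and exploratory efficacy summaries after it.

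The conclusion rests on the wording of the listed conditions. The 8.5 patient-years is a ceiling on uncovered time, not an estimate of cases.

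**What to change.** In Section 7.1.2.2 and the protocol summary, replace the condition with: *Disease progression (AP/BC) documented at any time before the first dose of asciminib, based on all results available before that dose, including EOT assessments completed late and any repeat tests.* State that the last-test rule applies to the peripheral-blood AP/BC criteria, with thrombocytopenia still needing attribution as unrelated to therapy. Align the IRT check if it does not already do this.

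The cost is one condition, one clause and possibly one system check. Because the rule uses results already available, it needs no new sample. It does not guarantee a same-day blood count: S-Week 1 Day 1 haematology is analysed centrally (Section 7.2.2.5.1) and nothing says the result is back before the dose. Requiring that result first would be a further step and could need an extra local test. The downside is that a few patients lose the switch and enter survival follow-up, as the section already provides.

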7.1.2.3 Information to be collected on screening failures

Patients who sign an informed consent but fail to be randomized for any reason will be considered a screen failure. The reason for not being randomized will be entered on the Screening Phase Disposition Page. The demographic information, informed consent, and Inclusion/Exclusion pages must also be completed for Screen Failure patients. No other data will be entered into the clinical database for patients who are screen failures, unless the patient experienced a Serious Adverse Event during the Screening Phase (see [Section 8](#) for SAE reporting details). If the patient fails to be randomized, the IRT must be notified within 2 days of the screen fail that the patient was not randomized.

7.1.2.4 Patient demographics and other baseline characteristics

Patient demographics and baseline characteristics collected will include the following: date of birth, gender (and child bearing potential for female), race and ethnicity, height, weight, all relevant medical history including cardiovascular disease history, CML disease history,

including mutation status, and prior and concomitant medication including prior TKI therapy and antineoplastic medication.

Physical examination including extramedullary involvement, performance status, vital signs, ECGs, and laboratory assessments will be performed at screening.

Significant findings that were present prior to the signing of informed consent must be included in the Relevant Medical History/Current Medical Conditions page on the subject's eCRF. Significant new findings that begin or worsen after informed consent must be recorded on the AE page of the patient's eCRF.

The central reading of the screening ECGs as well as the results of the RQ-PCR and the bone marrow aspirate must be available prior to randomization and first dose of study treatment to evaluate eligibility and to stratify the patient.

7.1.2.5 Local recruitment procedures-Japan

Given the limited safety data available in Japanese patients, specific recruitment and data monitoring procedures will be put in place for Japanese patients randomized to asciminib. Randomization of these patients will be staggered to avoid enrollment of more than one patient on the same day. Safety parameters from a minimum of 2 patients treated on the asciminib arm will be reviewed for determining the appropriateness of continuing patient enrollment in Japan.

7.1.3 Run-in period

Not applicable.

7.1.4 Treatment period

There is no fixed duration of treatment planned per patient. All patients will be given the opportunity to receive study treatment until the end of study treatment period as defined in (Section 4.3).

[figure not shown]
During the treatment phase, the patients will receive either asciminib treatment 40 mg BID or bosutinib 500 mg QD according to randomization. The dose can be modified, if required from the perspective of tolerance, following the guidance in Section 6.2 and Section 6.3. Treatment will be administered until patient experiences treatment failure, unacceptable toxicity, disease progression, death, lost to follow-up and/or treatment is discontinued at the discretion of the investigator or withdrawal of consent.

The patients are advised to adhere to the food restrictions during the treatment (fasting status regarding study treatment administration, avoidance of prohibited concomitant medication).

7.1.5 Visit windows

Study visits from Week 1 Day 1 to Week 2 Day 1 / S-Week 1 Day 1 to S-Week 2 Day 1 should be completed on the designated date [with an allowed "visit window" of +/- 1 day for Week 2 Day 1 / S-Week 2 Day 1]

Study visits from Week 4 to Week 16 / S-Week 4 to S-Week 16 should be completed every 2 weeks on the designated date [with an allowed "visit window" of +/- 1 day]

Study visits from Week 20 to Week 96 / S-Week 20 to S-Week 96 should be completed every 4 weeks on the designated date [with an allowed “visit window” of +/- 2 days]

Study visits from Week 108 to EOT / S-Week 108 to S-EOT should be completed every 12 weeks on the designated date [with an allowed “visit window” of +/- 7 days]

A delayed visit will have no impact on the next planned visit. The next visit should be completed as scheduled in order to avoid accumulation of additional weeks.

7.1.6 Discontinuation of study treatment

Patients may voluntarily discontinue from the study treatment for any reason at any time. If a patient decides to discontinue from the study treatment, the investigator should make a reasonable effort (e.g. telephone, e-mail, letter) to understand the primary reason for this decision and record this information in the patient’s chart and on the appropriate eCRF pages. They may be considered withdrawn if they state an intention to withdraw, fail to return for visits, or become lost to follow-up for any other reason.

The investigator should discontinue study treatment for a given patient if, he/she believes that continuation would be detrimental to the patient’s well-being. Patients who discontinue study treatment should undergo an end of treatment visit.

For patients who discontinue treatment in treatment period or switch treatment period for reasons other than death, lost to follow-up, or withdrawal of consent, the patient should enter the survival follow-up phase. Survival visit assessments (survival, antineoplastic therapies, stem cell transplant and progression) should be performed every 12 weeks until documented death, lost to follow-up, withdrawal of consent or until the end of the study. This visit can be conducted by telephone.

Patients who discontinue the study treatment for an adverse event suspected to be related to study drug or an abnormal laboratory value suspected to be related to study drug must be followed as described in [Section 8](#)

Patients may also be discontinued from the study treatment if any of the following occurs:

- discovery of patient ineligibility
- errors in treatment compliance [study treatment, other prescribed or non-prescribed medications]
- missed/unscheduled/off schedule/incomplete/incorrect assessments
- major protocol deviation
- use of prohibited treatment refer to [Section 14-Appendices](#)
- any other protocol deviation that results in a significant risk to the patient’s safety

In addition to the general discontinuation criteria, the following study specific criteria will also require discontinuation of study treatment:

- In the event of detection of T315I or V299L mutations at any time the patient **must** be discontinued from the study treatment.
- In the event of a pregnancy during study, if a patient wants to pursue the pregnancy then patient **must** be discontinued from the study treatment. However, in the event of a

spontaneous miscarriage or in the event of elective abortion, the patient is permitted to continue study treatment.

- In the event of treatment failure the patient must be discontinued from the study treatment. Patients randomized to bosutinib treatment experiencing treatment failure may switch to asciminib treatment. The following events will constitute ‘treatment failure’, and are based on the ELN criteria ([Baccarani et al 2013](#)) defining failure of a second line treatment:
 - No CHR or > 95% Ph+ metaphases at three months after initiation of therapy or thereafter
 - BCR-ABL1 ratio > 10% IS and/or > 65% Ph+ metaphases at six months after initiation of therapy or thereafter
 - BCR-ABL1 ratio > 10% IS and/or > 35% Ph+ metaphases at 12 months after initiation of therapy or thereafter
 - Loss of CHR, CCyR or PCyR at any time after initiation of therapy
 - Detection of new BCR-ABL1 mutations which potentially cause resistance to study treatment (asciminib or bosutinib) at any time after initiation of therapy
 - Confirmed loss of MMR in 2 consecutive tests ([Section 7.2.1.1](#))
 - New clonal chromosome abnormalities in Ph+ cells: CCA/Ph+: at any time after initiation of therapy
- In the event of disease progression the patient must be discontinued from the study treatment. The following events are considered disease progression.
 1. CML-related death (any death during treatment or follow-up if the principal cause of death is marked as “study indication” in the eCRF by the investigator, or if the death occurred subsequent to documented progression to AP/BC and the cause of death is reported as “unknown” or not reported by the investigator)
 2. Accelerated phase (AP) as defined by any of the following:
 - $\geq 15\%$ blasts in the peripheral blood or bone marrow aspirate, but $< 30\%$ blasts in both the peripheral blood and bone marrow aspirate
 - $\geq 30\%$ blasts plus promyelocytes in peripheral blood or bone marrow aspirate
 - $\geq 20\%$ basophils in the peripheral blood
 - Thrombocytopenia ($< 100 \times 10^9/L$) that is unrelated to therapy
 3. Blast crisis (BC) as defined by any of the following:
 - $\geq 30\%$ blasts in peripheral blood or bone marrow aspirate
 - Appearance of extramedullary involvement other than hepatosplenomegaly proven by biopsy (i.e., chloroma).

